**Author:**   
H2O Clinical, LLC  
[name]  
[name] 21031

**Version:** Final 2.0

**Release Date** July 02, 2020  
**NCT Number:** NCT03799627

---

Revision History

| Version   | Version Date     | Author | Summary of Changes Made   |
|-----------|------------------|--------|---|
| Draft 0.1 | 09 July 2018     |        | New Document  |
| Draft 0.2 | 20 July 2018     |        | Per sponsor's comments  |
| Draft 0.3 | 11 August 2018   |        | Per sponsor's comments  |
| Draft 0.4 | 13 January 2019  |        | Per sponsor's comments  |
| Draft 0.5 | 27 February 2019 |        | Per sponsor's comments  |
| Draft 0.6 | 16 April 2019    |        | Added new QoL assessment  |
| Draft 0.7 | 19 July 2019     |        | Per sponsor's comments  |
| Final 1.0 | 24 July 2019     |        | Added section 9.5 for any potential sensitivity analyses.
Modified the definition of PK population per [name].  |
| Final 2.0 | 02 July 2020     |        | Updated based on Protocol amendment 2, no IA analyses for the study. Added sensitivity analyses by excluding some HB data due to the Eurofins Ransomware Attack |

Statistical Analysis Plan  
Protocol No. AKB-6548-CI-0025

Akebia Therapeutics, Inc.

---

## LIST OF ABBREVIATIONS AND DEFINITIONS OF TERMS

|                     |   |
|---------------------|---|
| AE                  | adverse event   |
| ALP                 | alkaline phosphatase  |
| ALT                 | alanine aminotransferase  |
| AST                 | aspartate aminotransferase  |
| AUC inf  | area under concentration-time curve from dosing to infinity   |
| AUC last | area under concentration-time curve from dosing to last measurable concentration                    |
| BLQ                 | below the limit of quantification   |
| BP                  | blood pressure  |
| CBC                 | complete blood count  |
| CKD                 | chronic kidney disease  |
| CL/F                | apparent total body clearance   |
| C max    | maximum concentration   |
| CRF                 | Case Report Form  |
| CRO                 | Contract Research Organization  |
| CRP                 | C-reactive protein  |
| CTCAE               | common terminology criteria for adverse events  |
| CVD                 | cardiovascular disease  |
| DD-CKD              | dialysis dependent chronic kidney disease   |
| ECG                 | electrocardiogram   |
| EDC                 | electronic data capture   |
| EOT                 | end-of-treatment  |
| EPO                 | erythropoietin  |
| ESA                 | erythropoiesis-stimulating agent  |
| ESRD                | end-stage renal disease   |
| FAS                 | Full Analysis Population  |
| FSH                 | follicle stimulating hormone  |
| GCP                 | Good Clinical Practice  |
| Hb                  | hemoglobin  |
| HF                  | heart failure   |
| HIF                 | hypoxia-inducible factor  |
| HIF-PH              | hypoxia-inducible factor prolyl-hydroxylase   |
| HIF-PHI             | hypoxia-inducible factor prolyl-hydroxylase inhibitor   |
| HR                  | heart rate  |
| ICH                 | International Council for Harmonisation of Technical Requirements for Pharmaceuticals for Human Use |
| IRB                 | Institutional Review Board  |
| IV                  | intravenous   |
| IWRS                | Interactive Web Response System   |
| LFT                 | liver function test   |
| LPO                 | last patient out  |

---

|                  |   |
|------------------|---|
| MedDRA           | Medical Dictionary for Regulatory Activities  |
| mRNA             | messenger ribonucleic acid                    |
| MCS              | mental component score                        |
| NDD-CKD          | non-dialysis dependent chronic kidney disease |
| PCS              | physical component score                      |
| PD               | pharmacodynamics(s)                           |
| PGI-C            | patient global impression of change           |
| PGI-S            | patient global impression of severity         |
| PHD              | prolyl 4-hydroxylase domains                  |
| PI               | Package Insert                                |
| PK               | pharmacokinetic(s)                            |
| RBC              | red blood cell                                |
| RR               | respiratory rate                              |
| SAE              | serious adverse event                         |
| SD               | standard deviation                            |
| SGOT             | serum glutamic oxaloacetic transaminase       |
| SGPT             | serum glutamic pyruvic transaminase           |
| SO2              | oxygen saturation                             |
| TIW              | three times a week                            |
| T max | time to reach C max                |
| TSAT             | transferrin saturation                        |
| U                | unit  |
| ULN              | upper limit of normal                         |
| US               | United States                                 |
| Vd/F             | apparent volume of distribution               |
| VEGF             | vascular endothelial growth factor            |
| λ z   | elimination rate constant                     |

---

## 1 INTRODUCTION

The purpose of this statistical analysis plan (SAP) is to describe the procedures and the statistical analysis methods that will be used to analyze, and report results for Akebia Protocol AKB-6548-CI-0025.

This document is prepared based on the final study protocol Amendment 2, version 3 (dated April 05, 2019). Reader can refer to the study protocol, the case report form (CRF), and general CRF completion guidelines for details of study design, conduct and data collection. Specifications of tables, figures, and data listings are contained in a separate document.

---

## 2 STUDY OBJECTIVE AND DESIGN

### 2.1 Study Objectives

#### 2.1.1 Primary Objective

To assess the efficacy and safety of daily dosing of vadadustat compared to epoetin alfa for 12 weeks in hemodialysis subjects.

#### 2.1.2 Secondary Objectives

- To assess the efficacy and safety of TIW dosing of vadadustat in selected hemodialysis subjects who have been successfully managed with daily dosing of vadadustat through Week 12.
- To evaluate the PK/PD of daily and TIW dosing of vadadustat in hemodialysis subjects compared to epoetin alfa.
- To assess the efficacy and safety of several dosing strategies of vadadustat compared to epoetin alfa during a 20-week Treatment Period in hemodialysis subjects.

---

[figure not shown]
### **3 STUDY DESIGN**

This is a Phase 2, randomized, open-label study to evaluate vadadustat for the treatment of anemia in hemodialysis subjects converting from epoetin alfa therapy.

For all subjects (Main study and ESA hyporesponder parallel study), the study (as shown in [Figure 1](#)) will include a Screening Period, a study Treatment Period, and a Safety Follow-Up Period as described below.

The aim is to achieve and maintain Hb levels within the target range of 10.0 to 11.0 g/dL, inclusive, while targeting the middle of the range and minimizing excursions outside the target range.

**Figure 1: Overview of Study Design**

### **3.1 Screening Period (up to 28 days; Day -28 to Baseline/Day 1)**

For all subjects (Main study and ESA hyporesponder parallel study), the Screening Period starts at the time the informed consent is signed and will be a maximum of 28 days in duration. Baseline/Day 1 will be performed within 28 days of the start of Screening. Subjects who meet all eligibility criteria will be randomized to a vadadustat treatment arm or an epoetin alfa treatment arm. Subjects will be required to stop epoetin alfa treatment for a minimum duration of 5 days before Baseline/Day 1 in the Main study and for a minimum of 2 days before Baseline/Day 1 in the ESA hyporesponder parallel study. In the Main study, randomization will be stratified by the mean weekly epoetin dose calculated over a period of 8 weeks prior to Screening Visit 2 (SV2):

- Low epoetin alfa dose group ( $\leq 90$  U/kg/week)
- High epoetin alfa dose group ( $>90$  to  $<300$  U/kg/week)

### **3.2 Study Treatment Period (Baseline/Day 1 to Week 20)**

For all subjects (Main study and ESA hyporesponder parallel study), the Treatment Period will run from Baseline/Day 1 to Week 20. Dose will be adjusted to achieve and maintain Hb levels within the target range of 10.0 to 11.0 g/dL, inclusive, while targeting the middle of the range and minimizing excursions outside of the target range.

### **3.3 Vadadustat Treatment**

#### Subjects in the Main study randomized to vadadustat:

- Subjects in the low epoetin alfa dose group will start vadadustat at an initial, randomly allocated dose of 300 or 450 mg daily.
- Subjects in the high epoetin alfa dose group will start vadadustat at an initial, randomly allocated dose of 300, 450, or 600 mg daily.

#### Subjects in the ESA hyporesponder parallel study randomized to vadadustat:

- Subjects will receive a starting dose of vadadustat 600 mg daily.

#### Transition to TIW for all subjects randomized to vadadustat:

All subjects randomized to vadadustat (Main study and ESA hyporesponder parallel study), who complete the 12-week once daily dosing regimen and who meet all the Week 12 transition criteria for switching from daily to TIW dosing, will initiate TIW dosing at a starting dose one tablet greater (+150 mg) than the final dose in the daily dosing.

---

**Note:** Subjects who are not eligible to switch from daily vadadustat to TIW dosing at Week 12 will remain on daily dosing for the remainder of the study.

### **3.4 Epoetin Alfa Treatment**

Subjects in both the Main study and ESA hyporesponder parallel study randomized to epoetin alfa:

All subjects randomized to epoetin alfa will receive TIW dosing for the entire Treatment Period based on the subject's central laboratory Hb value and the approved epoetin alfa US Package Insert (PI) for adult patients with CKD on dialysis. Dose will be adjusted to achieve and maintain Hb levels within the target range of 10.0 to 11.0 g/dL, inclusive, while targeting the middle of the range and minimizing excursions outside of the target range.

### **3.5 Safety Follow-Up Period (Weeks 20 to 24)**

For all subjects (Main study and ESA hyporesponder parallel study), the 4-week Safety Follow-Up Period starting at Week 20 will be followed by a post-treatment safety assessment conducted at the beginning of Week 24.

### **3.6 Study Medication Stopping Rules**

Study medication must be permanently discontinued if a subject meets one of the following criteria:

- ALT **or** AST >3x Upper Limit of Normal (ULN) **and** total bilirubin >2x ULN
- ALT **or** AST >3x ULN **and** international normalized ratio (INR) >1.5
- ALT **or** AST >8x ULN
- ALT **or** AST remains >5x ULN over 2 weeks
- ALT or AST >3x ULN with symptoms (e.g., fatigue, nausea, vomiting, right upper quadrant pain, fever, rash) or eosinophilia.

---

#### 4 CHANGES FROM THE PROTOCOL

No changes in planned analyses were done compared to the protocol in this SAP. But due to the Eurofins Ransomware Attack, the change from baseline in Hemoglobin (Hb, g/dL) with excluding subjects who were randomized before July 23, 2019 for vadadustat group will be provided as sensitivity analyses.

---

## 5 PRIMARY AND SECONDARY ENDPOINTS

### 5.1 Primary Efficacy Endpoint

The primary endpoint will be the mean change in Hb between Baseline (average pretreatment Hb) and the primary evaluation period (average Hb from Weeks 10 to 12).

### 5.2 Key Secondary Efficacy Endpoints

- Proportion of subjects with Hb values within the target range (10.0 to 11.0 g/dL, inclusive) at the primary evaluation period (Weeks 10 to 12).
- For subjects who transitioned to TIW vadadustat dosing, mean change in Hb from primary evaluation period (average Hb from Weeks 10 to 12) to the secondary evaluation period (average Hb from Weeks 18 to 20).

### 5.3 Other Secondary Efficacy Endpoints

- Mean change in Hb between Baseline (average pretreatment Hb) and the secondary evaluation period (average Hb from Weeks 18 to 20)
- Proportion of subjects with Hb values within the target range (10.0 to 11.0 g/dL, inclusive) at the secondary evaluation period (Weeks 18 to 20)
- For subjects who transitioned to TIW vadadustat dosing, proportion of subjects with Hb values within the target range (10.0 to 11.0 g/dL, inclusive) at the secondary evaluation period (Weeks 18 to 20)
- Proportion of subjects with a mean increase in Hb from Baseline to the primary evaluation period  $\geq 0.5$  g/dL (average Hb from Weeks 10 to 12) or with Hb values within the target range (10.0 to 11.0 g/dL, inclusive) at the primary evaluation period (Weeks 10 to 12)
- Proportion of subjects with a mean increase in Hb from Baseline to the secondary evaluation period  $\geq 0.5$  g/dL (average Hb from Weeks 18 to 20) or with Hb values within the target range (10.0 to 11.0 g/dL, inclusive) at the secondary evaluation period (Weeks 18 to 20)
- Intravenous (IV) iron supplementation
- ESA rescue
- RBC transfusion

### 5.4 Exploratory Endpoints

## 5.5 PK/PD Endpoints

The PK parameters will include (but not limited to) the following:

- Area under concentration-time curve from dosing to last measurable concentration (AUClast)
- Area under concentration-time curve from dosing to infinity (AUCinf)
- Maximum concentration Cmax
- Time to reach Cmax (Tmax)
- Apparent total body clearance (CL/F)
- Apparent volume of distribution (Vd/F)
- Terminal half-life (t1/2)

The PD parameters will include (but are not limited to) the following:

- EPO
- Reticulocytes
- Iron
- Ferritin
- TIBC
- Hepcidin

## 5.6 Safety Endpoints

Safety endpoints in this study include the following:

- AEs
- Vital sign measurements and clinical laboratory values
- Hb >12.0 g/dL, >13.0 g/dL, or >14.0 g/dL
- Hb <8.0 g/dL and decline in Hb  $\geq$ 0.5 g/dL from Baseline Hb (Main Study);
- Hb <7.5 g/dL and decline in Hb  $\geq$ 0.5 g/dL from Baseline Hb (ESA hyporesponder parallel study)
- Hb increase >1.0 g/dL within any 2-week interval

---

## 6 GENERAL ANALYSIS DEFINITION

Data collected throughout the study will be summarized using descriptive statistics and listed in the by-subject listings. The continuous variables will be summarized by descriptive statistics (n, mean, SD, median, minimum, and maximum). Categorical variables will be summarized with frequency and percentage. Summaries will be provided by treatment group within appropriate analysis populations, and by time point/time period, as appropriate. Baseline is defined as the last observation before the first dose of study drug administration except for the parameters specified below.

Primary evaluation period is defined as Weeks 10 to 12 and the secondary evaluation period is defined as Weeks 18 to 20.

Study day is defined as follows:

Study Day= [Event date – First dosing date + 1] if after first dosing date  
[Event date – First dosing date] if before first dosing date.

Note that with the definition above, days of "0" will not be used. As such, the study day can be interpreted as the number of days before or after first day of dosing. Event date refers to the date associated with the result being summarized. In some cases, this is the date of an assessment or measurement; in other cases, this is the onset date of an adverse or outcome event.

Assessments will be assigned to analysis visits based on the date the assessment took place regardless of the CRF page completed (i.e., scheduled visit number). Assessments will be mapped to visits based on Study Day.

If more than 1 Hb result is available in an analysis time period post-baseline, the average of all observed values will be assigned to that period. When more than 1 assessment is made for other measures within a given visit window post-baseline, the value of the assessment closest to the scheduled visit should be used. If the assessments are equally close, the value from the last assessment should be used.

If the central laboratory uses assays that have lower limits of detection (LLD), all laboratory results below the LLD will be imputed with the LLD. Results reported as greater than a value (i.e., “> value”) will be imputed as  $1.5 \times$  that value.

For subjects whose reference date is missing, the study day will also be categorized as missing.

*Adverse event onset*

- If onset date is completely missing, date is set to date of first dose.
- If year is present and month and day are missing or year and day are present and month is missing:

---

- If year = year of first dose, then set month and day to month and day of first dose.
- If year < year of first dose, then set month and day to December 31.
- If year > year of first dose, then set month and day to January 1.
- If month and year are present and day is missing:
  - If year = year of first dose and
    - month = month of first dose, then set day to day of first dose date.
    - month < month of first dose, then set day to last day of month.
    - month > month of first dose, then set day to first day of month.
  - If year < year of first dose, then set day to last day of month.
  - If year > year of first dose, then set day to first day of month.
- For all other cases, set date to date of first dose.

*Adverse event end date*

- If year is present and month and day are missing or year and day are present and month is missing, set end month and day to December 31.
- If month and year are present and day is missing, set the day to last day of the month.
- If fatal event, date is set to minimum of imputed end date and death date.
- For all other cases, set date to missing.

The following [table](#) provides the convention to classify assessment dates into protocol-defined visits. The time windows reflect the administrative range around each visit. These windows are wider than those stated in the protocol.

Table 1. Classification of assessments at every visit during the study

| Target week / day                  | Actual visit day              | Visit / Week classification    |
|------------------------------------|-------------------------------|--------------------------------|
| Week 0 / Day 1                     | Day 1                         | Visit 1 / Week 0               |
| Week 1 / Day 8                     | Day 2-11                      | Visit 2 / Week 1               |
| Week 2 / Day 15                    | Day 12-21                     | Visit 3 / Week 2               |
| Week 4 / Day 29                    | Day 22-35                     | Visit 4 / Week 4               |
| Week 6 / Day 43                    | Day 36-49                     | Visit 5 / Week 6               |
| Week 8 / Day 57                    | Day 50-63                     | Visit 6 / Week 8               |
| Week 10 / Day 71                   | Day 64-74                     | Visit 7 / Week 10              |
| Week 11 / Day 78                   | Day 75-81                     | Visit 8 / Week 11              |
| Week 12 / Day 85                   | Day 82-88                     | Visit 9 / Week 12              |
| Week 13 / Day 92                   | Day 89-95                     | Visit 10 / Week 13             |
| Week 14 / Day 99                   | Day 96-105                    | Visit 11 / Week 14             |
| Week 16 / Day 113                  | Day 106-119                   | Visit 12 / Week 16             |
| Week 18 / Day 127                  | Day 120-133                   | Visit 13 / Week 18             |
| Week 20 / Day 141                  | Day 134 - (last dose day + 7) | Visit 14 / Week 20             |
| Follow up / Day last dose day + 28 | ≥ last dose day + 8           | Visit 15 / Week 24 (Follow up) |

Note: Week 20 is the end of treatment.

It is expected that some subjects will discontinue Follow-Up. The reasons for any missing data will be summarized by treatment arm. The primary analysis will be based upon observed data without imputation. As a sensitivity analysis for primary efficacy endpoint, missing Hb in weeks 10 to 12 will be imputed using last observation carried forward (LOCF). Similarly, for certain secondary efficacy endpoints, missing Hb in weeks 18-20 will be imputed using LOCF.

---

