| Score                        | Calculation  |
|------------------------------|--|
| Aggregate Standardized Score |  |
| Mental component             | $\text{AGG\_MENT} = (\text{PF\_Z} * -0.22999) + (\text{RP\_Z} * -0.12329) + (\text{BP\_Z} * -0.09731) + (\text{GH\_Z} * -0.01571) + (\text{VT\_Z} * 0.23534) + (\text{SF\_Z} * 0.26876) + (\text{RE\_Z} * 0.43407) + (\text{MH\_Z} * 0.48581)$ |
| Transformed Summary          |  |
| Transformed physical         | $\text{PCS} = 50 + (\text{AGG\_PHYS} * 10)$  |
| Transformed mental           | $\text{MCS} = 50 + (\text{AGG\_MENT} * 10)$  |

For each of the 8 dimensions, if less than 50% of the items which constitute that dimension are missing, the dimension score will be calculated by the mean of the available non-missing items. The physical health composite summary (PCS) and mental health composite summary (MCS) will only be calculated if a score has been calculated for all 4 dimensions that constitute the composite summary.

The physical component score (PCS) includes 4 domains of the SF-36: (1) physical functioning (PF); (2) role limitations due to physical health problems (RP); (3) bodily pain (BP) and (4) general health perceptions (GH); while the mental component score (MCS) includes the other 4 domains. The mean change in these endpoints at weeks 12, 20, and 24 will be summarized by treatment group with descriptive statistics.

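### A Week 12 SF-36 completed 4 or more days off target is relabelled by Table 1 to a week with no SF-36 summary, and nothing in the SAP brings it back

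*SAP*

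**What the plan says.** SAP section 6 (General Analysis Definition) sets the mapping rule: "Assessments will be assigned to analysis visits based on the date the assessment took place regardless of the CRF page completed". It adds: "Assessments will be mapped to visits based on Study Day". The windows stand in a single table, "Table 1. Classification of assessments at every visit during the study", and no measure has windows of its own. Around the end of daily dosing the table reads:

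- Week 11: target Day 78, window Day 75-81
- Week 12: target Day 85, window Day 82-88
- Week 13: target Day 92, window Day 89-95

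The text introducing the table says of the windows: "These windows are wider than those stated in the protocol". A note under it fixes the last on-treatment visit: "Note: Week 20 is the end of treatment".

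For SF-36, section 9.4.1 states: "The mean change in these endpoints at weeks 12, 20, and 24 will be summarized by treatment group with descriptive statistics". No other SF-36 time point is named.

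Two rules might be expected to help a mistimed form. The closest-value rule in section 6 begins "When more than 1 assessment is made for other measures within a given visit window post-baseline", so it chooses among values inside one window. The LOCF rule in sections 6 and 9 is written for Hb only.

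**The concern.** Adjoining 7-day windows do little harm to Hb. The primary endpoint averages Hb over Weeks 10 to 12, so a value moved from Week 12 to Week 11 still counts in the evaluation period. A value moved to Week 13 leaves the period, but the subject's other Hb values in it remain.

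SF-36 has no such averaging. Its Week 12 summary needs a form dated Day 82-88. A form completed on Day 81 or Day 89 is given a week label at which SF-36 is not summarised, even though the CRF identifies it as the Week 12 questionnaire. A timing deviation of a few days then becomes a missing value.

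Week 12 is the end of the daily-dosing comparison named in the primary objective, and it is the only SF-36 summary point before end of treatment. At stake is the completeness of that one table. No inferential result depends on it.

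**Working it through.** **Inputs.** The windows come from Table 1 in SAP section 6, and the SF-36 time points from section 9.4.1. The SAP gives no data on actual visit timing.

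**Step 1: the Week 12 window.** The target is Day 85. 85 - 3 = 82 and 85 + 3 = 88, so Day 82-88 is a tolerance of -3/+3 days. The on-treatment windows meet without gaps, so every day outside Day 82-88 belongs to another week.

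**Step 2: where a mistimed Week 12 form goes.** Each Study Day from 70 to 100 was mapped through Table 1.

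| Days from Day 85 | Study Day | Analysis week | SF-36 summary? |
|---|---|---|---|
| -15 to -11 | 70-74 | Week 10 | no |
| -10 to -4 | 75-81 | Week 11 | no |
| -3 to +3 | 82-88 | Week 12 | yes |
| +4 to +10 | 89-95 | Week 13 | no |
| +11 to +15 | 96-100 | Week 14 | no |

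Within the range checked, every form 4 or more days off target leaves Week 12 and reaches no SF-36 summary point.

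**Step 3: whether another rule recovers it.** The closest-value rule works inside one window, so it cannot move a Day 89 form from Week 13 to Week 12. LOCF covers Hb only. The CRF visit label is expressly overridden. No recovery rule remains.

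**Step 4: how Week 12 compares with other windows.** Table 1 has 13 on-treatment visits after baseline. Five of them (Weeks 4, 6, 8, 16 and 18) allow -7/+6 days. Week 20 allows 7 days early, with a late limit tied to the last dose. The other seven (Weeks 1, 2, 10, 11, 12, 13 and 14) are limited to 3 days on at least one side. Only Weeks 11, 12 and 13 are limited to 3 days on both sides.

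**Step 5: illustrative size.** Assume that the deviation from Day 85 is normal with mean 0 and standard deviation SD, rounded to whole days. A form is then lost when the unrounded deviation exceeds 3.5 days in either direction:

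P(lost) = 2 × [1 - Φ(3.5 / SD)]

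| Assumed SD (days) | 3.5 / SD | P(lost) | Of 95 planned Main-study subjects |
|---|---|---|---|
| 1 | 3.50 | 0.05% | about 0 |
| 1.5 | 2.33 | 2.0% | 1.9 |
| 2 | 1.75 | 8.0% | 7.6 |
| 3 | 1.17 | 24.3% | 23.1 |

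The last column assumes that all 95 subjects complete a Week 12 form. The SDs are assumptions, and nothing in the SAP favours one over another.

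**The case against.** The strongest point on the other side is the SAP's own statement that its windows exceed the protocol's. If that holds at Week 12, a visit made inside the protocol window keeps its label, and only out-of-window visits can be relabelled. This stands and limits the frequency, possibly to very few forms. It does not remove the gap: analysis windows are widened to keep off-schedule visits in the tables, and at Week 12 this works only up to 3 days.

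It is also fair to say that mapping by date with contiguous windows is conventional, that 7-day windows follow naturally from visits a week apart, and that a narrow Week 12 keeps the summary close to the pre-switch state. The last of these argues against a very wide window. It does not argue against keeping a form collected at the Week 12 visit.

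A reader might infer more than the text supports:

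- **That 8% to 24% of forms will be lost.** Those figures come from assumed SDs. If the SAP windows are indeed the wider ones, they imply that at least that share of visits misses the protocol window, and the SAP offers no evidence of this.
- **That the data are discarded.** Section 6 provides for by-subject listings, so a form leaves the summary table only.
- **That the loss biases the comparison.** Late visits might follow illness, but the SAP shows nothing either way.
- **That other non-Hb measures suffer too.** This depends on collection schedules that are not shown.
- **That Week 12 is singled out against mostly wide windows.** Step 4 of the working shows only five at -7/+6.

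**Conclusion.** The point holds as a minor one. Under sections 6 and 9.4.1 read together, a Week 12 SF-36 completed 4 or more days from Day 85 drops out of the only SF-36 summary before end of treatment, and no rule in the SAP restores it. This follows from the text without any assumption.

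The number affected cannot be determined from the SAP. It is confined to visits outside the protocol window, provided that the SAP's statement about window widths is correct for Week 12. The range in Step 5, from almost none at an SD of 1 day to about a quarter at 3 days, shows only how strongly the answer depends on visit timing.

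The consequence is small. SF-36 is an exploratory measure summarised descriptively, and the Hb analyses are untouched.

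**What to change.** Keep Table 1 as it stands for Hb. Add one rule for the SF-36 Week 12 summary, to apply when a subject has no form in Day 82-88. Choose one of two options and fix it before the tables are programmed:

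1. Use the form collected at the nominal Week 12 visit, as labelled on the CRF.
2. Use the form nearest Day 85 within a wider SF-36 window such as Day 75-95, which is 85 - 10 to 85 + 10 and covers the present Week 11 to Week 13 windows.

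In either case, flag any form completed after the first TIW dose, so that the reader can see which Week 12 values no longer reflect daily dosing only.

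Cutting at the midpoint between SF-36 time points is not advised. (85 + 141) / 2 = 113, so Week 12 would run to about the Week 16 target, 28 days past its own, and could take in forms completed well after the switch.

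The cost is one sentence or a short extra table in section 6 and one flag variable. The downside is a slightly wider spread of completion dates at Week 12.

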### 10.1 Adverse Events

Safety analyses will be descriptive in nature.

All AEs will be coded using MedDRA version 23.0.

An AE (classified by preferred term) started during the treatment period will be considered a treatment-emergent adverse event (TEAE) if it was not present prior to the first dose of study medication, or it was present prior to the first dose of study medication but increased in severity during the treatment period. An AE that occurs more than 28 days after the last dose of study medication will not be counted as a TEAE.

The number and percentage of subjects reporting TEAEs in each treatment group and each treatment period will be tabulated by system organ class and preferred term; by system organ class, preferred term, and severity; and by system organ class, preferred term, and relationship to study medication. If more than one event occurs with the same preferred term for the same patient, the patient will be counted only once for that preferred term using the most severe and most related occurrence for the summarization by severity and by relationship to the study medication.

The distribution of TEAEs by severity and relationship to study medication will be summarized by SOC and PT and treatment group. AEs will also be summarized by their maximum severity.

Summaries will also be provided for the following types of TEAEs:

- SAEs
- Related TEAEs, as determined by the Investigator
- TEAEs leading to early discontinuation of study drug
- Adverse events of special interest (AESI); AESI is defined in [Appendix 4](#).

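### Four adverse-event onset rules impute the first-dose date without checking the end date, so an event known to have resolved before dosing can be dated to Day 1 and enter the treatment-emergent tables

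*SAP*

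**What the plan says.** The onset rules in SAP section 6 (General Analysis Definition, adverse event onset) contain four branches that end at the first-dose date:

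- Nothing known: "If onset date is completely missing, date is set to date of first dose".
- Month missing, with or without a day: "If year = year of first dose, then set month and day to month and day of first dose".
- Day missing, same year as first dose: "month = month of first dose, then set day to day of first dose date".
- Anything not covered: "For all other cases, set date to date of first dose".

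Other branches keep an onset before dosing when the known part of the date shows it. For an earlier month in the dosing year: "month < month of first dose, then set day to last day of month". For an earlier year with no month: "If year < year of first dose, then set month and day to December 31".

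End dates are imputed in a separate block, to the end of the month or the end of the year, and otherwise set to missing. The only comparison made there is with death: "If fatal event, date is set to minimum of imputed end date and death date".

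Section 10.1 has two parts to its definition of a treatment-emergent event. The event must begin within the treatment period, and it qualifies "if it was not present prior to the first dose of study medication", or if it was present earlier and then became more severe.

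**The concern.** Dating an unknown onset to first dose is a common cautious choice when nothing in the record contradicts it. Here the rule also applies when something does. A recorded end date before first dose shows that the whole event preceded treatment, yet the imputed onset falls on Day 1, after the event was over.

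At stake are the by-arm counts of treatment-emergent events and of events of special interest (section 10.1 and Appendix 4), including the set of safety tables for the first 12 weeks in section 8.1. The arms are small, so a single subject shows as a visible percentage. The study is also open-label (section 3), which is a reason to settle the classification in writing rather than record by record.

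**Working it through.** **1. The rules applied to one record.** Take first dose on 20 August 2019 and a recorded end date of 10 August 2019 (illustrative dates).

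| Onset as recorded | Imputed onset | End minus onset | On or after first dose? |
|---|---|---|---|
| August 2019, day missing | 20 Aug 2019 | -10 days | Yes |
| 2019 only | 20 Aug 2019 | -10 days | Yes |
| Completely missing | 20 Aug 2019 | -10 days | Yes |
| July 2019, day missing | 31 Jul 2019 | +10 days | No |
| 2018 only | 31 Dec 2018 | +222 days | No |

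The first three rows are impossible date orders that the rules themselves create. The last two are classified correctly. The catch-all branch also assigns the first-dose date, so it behaves like the first three rows.

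**2. Carrying the date into section 10.1.** The treatment period runs from Baseline/Day 1 (section 3.2), so an onset on the first-dose date meets the requirement to begin within it. The second requirement, on presence before first dose, can be read in two ways:

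- From the imputed onset, the event was not present before first dose and counts as treatment-emergent.
- From the end date, it was present, ended and did not worsen on treatment, so it does not count.

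Nothing in section 6 or section 10.1 says which reading governs when onset is imputed.

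**3. How readily the rules misplace such a record.** Assumptions: every first-dose date in 2019; onset on each of days 28 to 2 before dosing, 28 days being the maximum screening length in section 3.1; resolution one day after onset, so always before first dose. This gives 365 × 27 = 9855 combinations.

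- *Day missing.* The record is moved when onset falls in the calendar month of first dose. Such combinations number 432 in a 31-day month, 405 in a 30-day month and 351 in February. The total is 7 × 432 + 4 × 405 + 351 = 4995, and 4995/9855 = 50.7%. The share depends on the day of the month of first dose: 3/27 on the 5th, 13/27 on the 15th, 26/27 on the 28th.
- *Month and day missing.* The record escapes only if onset fell in the previous calendar year, which is 405 combinations. So (9855 - 405)/9855 = 9450/9855 = 95.9%.
- *Completely missing.* 9855/9855 = 100%.

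These shares apply only to events that have an incomplete onset and were already over before dosing. They are not estimates of how many such records exist.

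**4. Weight of one subject.** Planned numbers are in section 7 and the arms in section 8.1. Equal allocation within each group is assumed.

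- Low-dose group: 40/3 = 13.3 per arm; one subject is 7.5 points.
- High-dose group: 55/4 = 13.75 per arm; one subject is 7.3 points.
- Hyporesponder study: 30/2 = 15 per arm; one subject is 6.7 points.

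If enrollment were raised by the full amount that section 7 allows, the hyporesponder arms would be (30 + 30)/2 = 30, or 3.3 points per subject. Main-study arms would average (95 + 20)/7 = 16.4, or 6.1 points.

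**The case against.** The strongest objection is that section 10.1 already protects the tables. An event with an end date before first dose was present before first dose and did not worsen afterwards, so it fails the second requirement whatever onset is imputed. A reader might infer from section 6 alone that such events become treatment-emergent outright. The documents do not support that: they leave the outcome open. What remains is that the SAP writes a rule producing a contradictory onset date and does not tie the second requirement to the end date. Two programmers could follow it and classify the same record differently.

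Several narrower points also stand:

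- Not every partial date is affected. An earlier month or year stays before dosing, and a later one goes to the first day of that month or year.
- A reader might infer that about half of all screening events with a missing day are wrongly moved. Averaging over a 30-day month and a full 28-day window does give 434/840 = 0.517. That figure includes events still ongoing at first dose or with no end date, for which the first-dose date is reasonable. Screening may also be shorter than 28 days.
- The SAP plans no table of event duration, so impossible date orders would show only in listings or derived data. The tables of related events are less exposed, because an investigator would seldom attribute an event that ended before dosing to the study drug.
- The imputation errs toward counting more events, and the safety analysis is descriptive, so no test or decision rule turns on it.
- The SAP does not say from when adverse events are recorded. Some pre-dose conditions may be held as medical history instead.

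**Conclusion.** The point holds as a minor one. Four onset branches can contradict a recorded end date, and the treatment-emergent definition does not say how to resolve the conflict. Events known to have ended before dosing can therefore enter the treatment-emergent and special-interest tables, though it is not established that they will.

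Only records with both an incomplete onset and an end date known to precede first dose are affected. The SAP does not give their number, and it is probably small. At the planned size, and if allocation is equal, one misclassified subject moves a by-arm percentage by about 7 points; in pooled columns the shift is smaller. Efficacy results are untouched.

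**What to change.** Add one condition to section 6, covering all four branches including the catch-all. If the event's end date, recorded or imputed under the existing end-date rules, is before first dose, set onset no later than that end date and classify the event as not treatment-emergent. Use the first-dose date only when the end date is missing or falls on or after first dose. A cross-reference in section 10.1 would make clear that the end date decides prior presence in these cases.

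No possible treatment-emergent event is lost. The existing rules already place a partial end date at its latest possible day, so the guard acts only when resolution before dosing is certain. The cost is a sentence in the SAP and one condition in the adverse-event derivation.
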